### 6.6.2. Deaths

The frequency (number and percentage) of patients in the safety analysis set who died during the study and who died within 28 days after last dose of study treatment as well as the primary reason for death, will be tabulated based on information from the ‘Notice of Death’ CRF, by treatment arm.

The frequency (number and percentage) of patients in the safety analysis set who died within 30 days of first dose of study treatment will also be provided.

Date and cause of death will be provided in individual patient data listing together with selected dosing information (study treatment received, date of first/last administration, dose).

### 6.6.3. Laboratory Data

Laboratory results will be converted to International System of Units (Système International d'unités, SI) units which will be used for applying toxicity grades and for all summaries.

As described in [Section 3.4](#), baseline will be defined as the last non-missing assessment performed on or prior to date of the first dose of study treatment (or prior to randomization for patients randomized but not dosed). If there are multiple assessments that meet the baseline definition on the same day without the ability to determine which was truly last, then the worst grade will be assigned as the baseline grade. Since a few CTCAE terms (including Hypo/Hypercalcemia and Activated Partial Thromboplastin) can be derived using several laboratory tests (analytes) refer to the section 2.3.7 of the “Pfizer Oncology CTCAE Grading Implementation Guidance for Laboratory Data” for determination of baseline CTCAE grade in this situation.

Laboratory results will be programmatically classified according to NCI-CTCAE version 4.03 grade. Non-numerical qualifiers will not be taken into consideration in the derivation of grade (eg, hypokalemia Grade 1 and Grade 2 are only distinguished by a non-numerical qualifier and therefore Grade 2 will not be derived). In summary statistics the number and percentage of patients corresponding to grades that only include non-quantitative criteria will be displayed as a blank or NA (not assessed) rather than 0. If there is any overlap between grade criteria (eg, CTCAE grading criteria for Creatinine Increased – a value can fall into one range based on comparison to ULN and another range based on comparison to baseline), the highest (worst) grade would be assigned to that record. Grade 5 is defined in the CTCAE criteria guidance as an event with an outcome of death. Since laboratory data does not collect an outcome, Grade 5 is not used when programmatically grading laboratory data.

Grade 0 or Outside Toxicity Reference (OTR) is not defined specifically in the CTCAE guidance. However, programmatically this is used as a category to represent those patients who did not meet any of the Grades 1 to 4 criteria. If the laboratory value is evaluable for CTCAE criteria grading (numeric value is present, valid units and ranges are present as required to allow conversion to standard units and grading), and does not qualify for any of the Grade 1-4 criteria for a given lab test, then the value is assigned as Grade 0 or OTR.

Abnormalities will be described using the worst grade post-baseline. When determining the maximum post-baseline grade for a given patient and CTCAE test, the maximum across all analytes and assessments contributing to that CTCAE test will be used. Several laboratory tests have bi-directional grading criteria defined so that both low (hypo) and high (hyper) values can be graded separately. Each criterion will be summarized separately. In the cases where a value is graded as a Grade 1, 2, 3, or 4 for one of the directions, that value will also be assigned as a Grade 0 for the opposite direction for that test. For example, a value meeting the criteria for Grade 3 Hypercalcemia will be classified as a Grade 0 Hypocalcemia. For CTCAE terms that can be derived using one of several laboratory tests, the maximum post-baseline grade for a given patient and CTCAE term will be the maximum across all possible laboratory tests.

For **WBC differential counts** (total neutrophil [including bands], lymphocyte, monocyte, eosinophil, and basophil counts), the absolute value will be used when reported by the lab. When only percentages are available (this is mainly applicable for neutrophils and lymphocytes, because the CTCAE grading is based on the absolute counts), the absolute value is derived as follows:

$$\text{Derived differential absolute count} = (\text{WBC count}) \times (\text{Differential \%value}/100).$$

If the investigator reports both the absolute and % value for Neutrophils or Lymphocytes from the same laboratory sample date and patient, ONLY the absolute value will be graded. The % value will not be graded in this scenario.

If the % value is converted to the differential absolute count for grading and the LLN for the differential absolute count is not available (only LLN for % is available) then Grade 1 will be assigned if the following conditions are met:

- Lymphocyte count decreased:
  - derived absolute count does not meet Grade 2-4 criteria, and
  - % value < % LLN value, and
  - derived absolute count  $\geq 800/\text{mm}^3$ .
- Neutrophil count decreased
  - derived absolute count does not meet Grade 2-4 criteria, and
  - % value < % LLN value, and
  - derived absolute count  $\geq 1500/\text{mm}^3$ .

For **calcium**, CTCAE grading is based on Corrected Calcium and Ionized Calcium. Corrected Calcium is calculated from Albumin and Calcium as follows:

- Corrected Calcium (mmol/L) = Calcium (mmol/L) + 0.02 [40 - Albumin (g/L)].

Laboratory toxicities will be tabulated using descriptive statistics (number of patients and percentages):

- Summary of laboratory parameters by worst CTCAE grade post-baseline table will include number and percentage of patients with Grade 0, 1, 2, 3, 4, and Grade 1-4 laboratory abnormalities.
- Shift table will summarize baseline CTCAE grade versus the worst post-baseline CTCAE grade.
- Patients who developed toxicities of grade  $\geq 3$  will also be listed.

Additional laboratory results that are not part of NCI-CTCAE will be presented according to the following categories overall: below normal limit, within normal limits, and above normal limits. In the unlikely event that for a given patient, clinically significant abnormalities are noted in both directions (eg, > Upper Limit of Normal (ULN) and < Lower Limit of Normal (LLN)), then both abnormalities are counted.

### **Drug Induced Liver Toxicity**

Alanine aminotransferase (ALT), aspartate aminotransferase (AST), Alkaline Phosphatase (ALP), and total bilirubin (TBILI) are used to assess possible drug induced liver toxicity. The ratios of test result over the ULN will be calculated and classified for these three parameters during the on-treatment period.

Summary of liver function tests will include the following categories. The number and percentage of patients with each of the following during the on-treatment period will be summarized by treatment arm:

- For patients with normal ALT, AST, and TBILI at baseline, (ALT or AST) > 3×ULN and TBILI > 2×ULN and ALP < 2×ULN or missing.
- For patients with ALT, AST, or TBILI above the ULN at baseline:
  - Preexisting AST or ALT baseline values above ULN: AST or ALT values >2 times the baseline values AND >3×ULN; or >8×ULN (whichever is smaller).
  - Preexisting values of TBILI above the normal range: TBILI level increased from baseline value by an amount of at least 1×ULN or if the value reaches >3×ULN (whichever is smaller).

An evaluation of Drug-Induced Serious Hepatotoxicity (eDISH) plot will also be created, with different symbols for different treatment arms, by graphically displaying:

- peak serum ALT(/ULN) vs peak total bilirubin (/ULN) including reference lines at ALT=3×ULN and total bilirubin=2×ULN.
- peak serum AST(/ULN) vs peak total bilirubin (/ULN) including reference lines at AST=3×ULN and total bilirubin=2×ULN.

In addition, a listing of all TBILI, ALT, AST and ALP values for patients with a post-baseline TBILI > 2×ULN, ALT > 3×ULN or AST > 3×ULN will be provided.

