##### 4.1. Inclusion Criteria

Subjects must meet all of the following inclusion criteria to be eligible for enrollment into the Intensive and Non-Intensive study (unless where indicated):

1. Subjects with untreated AML according to the World Health Organization (WHO) 2016 Classification, including those with:
  - AML arising from MDS or another antecedent hematologic disease (AHD).
  - AML after previous cytotoxic therapy or radiation (secondary AML).
  - FLT3+ AML, assuming the patient is not receiving and is not intended to receive FLT3 inhibitor therapy during study participation.
2.  $\geq 18$  years of age (In Japan,  $\geq 20$  years of age).
3. Adequate Organ Function as defined by the following:
  - Serum aspartate aminotransferase (AST) and serum alanine aminotransferase (ALT)  $\leq 3$  x upper limit of normal (ULN), excluding subjects with liver function abnormalities due to underlying malignancy.
  - Total serum bilirubin  $\leq 2$  x ULN (except subjects with documented Gilbert's syndrome).
  - Estimated creatinine clearance  $\geq 30$  mL/min as calculated using the standard method for the institution.

4. QTc interval  $\leq 470$  msec using the Fridericia correction (QTcF).
  - QTc criteria for eligibility does not apply to subjects with a functioning pacemaker, whether the rhythm is paced or not.
5. All anti-cancer treatments (unless specified) should be discontinued  $\geq 2$  weeks from study entry, for example: targeted chemotherapy, radiotherapy, investigational anti-cancer agents, hormones, or cytokines.
  - For control of rapidly progressing leukemia, hydroxyurea, and/or leukopheresis may be used before and for up to 1 week after the first dose of glasdegib. Continuation or resumption of hydroxyurea or leukopheresis after that time period must be approved by the Sponsor.
6. Serum or urine pregnancy test (for female subjects of childbearing potential) with a minimum sensitivity of 25 IU/L or equivalent units of human chorionic gonadotropin (hCG) negative at screening.
7. Male and female subjects of childbearing potential and at risk for pregnancy must agree to use at least one highly effective method of contraception throughout the study and for 180 days after the last dose of azacitidine, cytarabine, or daunorubicin; and the last dose of glasdegib or placebo, whichever occurs later.
8. Female subjects of non-childbearing potential must meet at least 1 of the following criteria:

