#### 8.4.2. Potential Cases of Drug-Induced Liver Injury

Humans exposed to a drug who show no sign of liver injury (as determined by elevations in transaminases) are termed "tolerators," while those who show transient liver injury, but adapt are termed "adaptors." In some subjects, transaminase elevations are a harbinger of a more serious potential outcome. These subjects fail to adapt and therefore are "susceptible" to progressive and serious liver injury, commonly referred to as drug-induced liver injury (DILI). Subjects who experience a transaminase elevation above 3 times the upper limit of normal ( $\times$  ULN) should be monitored more frequently to determine if they are an "adaptor" or are "susceptible."

In the majority of DILI cases, elevations in aspartate aminotransferase (AST) and/or alanine aminotransferase (ALT) precede total bilirubin (TBili) elevations ( $>2 \times \text{ULN}$ ) by several days or weeks. The increase in TBili typically occurs while AST/ALT is/are still elevated above  $3 \times \text{ULN}$  (ie, AST/ALT and TBili values will be elevated within the same lab sample). In rare instances, by the time TBili elevations are detected, AST/ALT values might have decreased. This occurrence is still regarded as a potential DILI. Therefore, abnormal elevations in either AST OR ALT in addition to TBili that meet the criteria outlined below are considered potential DILI (assessed per Hy's law criteria) cases and should always be considered important medical events, even before all other possible causes of liver injury have been excluded.

The threshold of laboratory abnormalities for a potential DILI case depends on the subject's individual baseline values and underlying conditions. Subjects who present with the following laboratory abnormalities should be evaluated further as potential DILI (Hy's law) cases to definitively determine the etiology of the abnormal laboratory values:

- Subjects with AST/ALT and TBili baseline values within the normal range who subsequently present with AST OR ALT values  $>3 \times \text{ULN}$  AND a TBili value  $>2 \times \text{ULN}$  with no evidence of hemolysis and an alkaline phosphatase value  $<2 \times \text{ULN}$  or not available;
- For subjects with baseline AST **OR** ALT **OR** TBili values above the ULN, the following threshold values are used in the definition mentioned above, as needed, depending on which values are above the ULN at baseline:

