All cases demonstrated on repeat testing as meeting the laboratory criteria of AST/ALT and TBili elevation defined above should be considered potential DILI (Hy's law) cases if no other reason for the LFT abnormalities has yet been found. **Such potential DILI (Hy's law) cases are to be reported as SAEs, irrespective of availability of all the results of the investigations performed to determine etiology of the LFT abnormalities.**

A potential DILI (Hy's law) case becomes a confirmed case only after all results of reasonable investigations have been received and have excluded an alternative etiology.

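### For subjects with raised baseline liver tests, the SAP's liver-toxicity table has only single-test rows, so no row counts by arm those meeting the protocol's joint potential-DILI laboratory criteria

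*SAP*

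**What the plan says.** Protocol 8.4.2 makes a potential DILI case joint: "abnormal elevations in either AST OR ALT in addition to TBili that meet the criteria outlined below are considered potential DILI". With normal baseline tests the rule is AST or ALT above 3×ULN and TBili above 2×ULN, no sign of hemolysis, and ALP below 2×ULN or unavailable. For subjects with a raised baseline test, "the following threshold values are used in the definition mentioned above, as needed, depending on which values are above the ULN at baseline". Adjusted AST/ALT and TBili thresholds follow. The section repeats the pairing where it deals with repeat testing: "All cases demonstrated on repeat testing as meeting the laboratory criteria of AST/ALT and TBili elevation defined above should be considered potential DILI".

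SAP 6.6.3 (Drug Induced Liver Toxicity) introduces its categories with "The number and percentage of patients with each of the following during the on-treatment period will be summarized by treatment arm". The first category is joint: "For patients with normal ALT, AST, and TBILI at baseline, (ALT or AST) > 3×ULN and TBILI > 2×ULN and ALP < 2×ULN or missing". Subjects with any of the three tests above ULN at baseline get two sub-bullets. One begins "Preexisting AST or ALT baseline values above ULN: AST or ALT values >2 times the baseline values AND >3×ULN" and adds an alternative of more than 8×ULN. The other begins "Preexisting values of TBILI above the normal range: TBILI level increased from baseline value by an amount of at least 1×ULN" and adds an alternative of more than 3×ULN. Neither mentions the other test or ALP, and the protocol's linking sentence is absent.

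The same section plans eDISH plots of peak ALT and peak AST against peak bilirubin, with reference lines at 3×ULN and 2×ULN and arms distinguished by symbol. It also plans a listing of all TBILI, ALT, AST and ALP values for anyone with a post-baseline TBILI above 2×ULN or an ALT or AST above 3×ULN.

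**The concern.** A threshold that substitutes for one part of a joint definition is not itself the definition. Once the linking sentence is dropped, a programmer following the SAP would build an AST/ALT-only row and a bilirubin-only row. An isolated rise in one test would then appear under the drug-induced liver toxicity heading in the same row as a subject in whom both tests rose.

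The subgroup can exist. Inclusion criterion 3 admits AST and ALT up to 3×ULN, "excluding subjects with liver function abnormalities due to underlying malignancy", and bilirubin up to 2×ULN with an exception for documented Gilbert's syndrome. At stake is the one programmed table that could show, by arm, how many subjects met the protocol's laboratory criteria. For these subjects it does not answer that question.

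**Working it through.** The plan states no figure here, so the check is to write both rules out and apply them to constructed subjects. All values are multiples of ULN and are hypothetical, not trial data.

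**Rules.** Let a0 and a be baseline and on-treatment ALT (AST works the same way), t0 and t the same for TBILI, and p the ALP.

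- AST/ALT criterion (Protocol 8.4.2): if a0 ≤ 1, a > 3; if a0 > 1, (a > 2·a0 and a > 3) or a > 8.
- TBILI criterion (Protocol 8.4.2): if t0 ≤ 1, t > 2; if t0 > 1, t − t0 ≥ 1 or t > 3.
- Protocol laboratory case: AST/ALT criterion AND TBILI criterion AND (p < 2 or missing).
- SAP AST/ALT row: a0 > 1 and the AST/ALT criterion. SAP TBILI row: t0 > 1 and the TBILI criterion.
- eDISH upper-right quadrant: a > 3 and t > 2. Listing: a > 3 or t > 2.

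**Constructed subjects.**

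| Subject | ALT | TBILI | ALP | Protocol case | SAP AST/ALT row | SAP TBILI row | eDISH quadrant |
|---|---|---|---|---|---|---|---|
| A | 2 → 5 | 0.8 → 0.8 | 1 | no | yes | no | no |
| B | 0.8 → 0.9 | 1.5 → 2.6 | 1 | no | no | yes | no |
| C | 2 → 5 | 0.8 → 2.5 | 1 | yes | yes | no | yes |
| D | 0.8 → 4 | 1.5 → 2.6 | 1 | yes | no | yes | yes |
| E | 2 → 5 | 1.5 → 2.6 | 1 | yes | yes | yes | yes |
| F | 2 → 5 | 0.8 → 2.5 | 3 | no | yes | no | yes |
| G | 2.5 → 4.5 | 0.8 → 2.5 | 1 | no | no | no | yes |

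For example, in A and C ALT meets its criterion because 5 > 2 × 2 = 4 and 5 > 3. In B, D and E bilirubin meets its criterion because 2.6 − 1.5 = 1.1 ≥ 1. All seven subjects enter the listing.

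**Reading the table.** The SAP rows cannot separate C from A, D from B, or C from F. Subject E is counted once in each row, with nothing to show that both criteria were met by one person.

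**Do the other outputs miss cases?** No. The adjusted AST/ALT criterion always implies a > 3. The adjusted TBILI criterion applies only when t0 > 1, so a rise of at least 1 gives t > 2, and the alternative is t > 3. The standard thresholds are 3 and 2 themselves. Every subject meeting the joint thresholds therefore lies in the upper-right quadrant of at least one plot and in the listing.

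**Do they include others?** Yes. F is in the quadrant although ALP is 3. G is in it although 4.5 is below 2 × 2.5 = 5.

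**With the joint row in place**, C, D and E are counted, and A, B, F and G are not.

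**The case against.** The strongest reply is that this is a dropped sentence in one descriptive table. The bullets nearly copy the protocol, the SAP says it supplements the protocol, and the rows are presented as a summary of liver function tests, not as Hy's law cases. Nothing in site case handling, SAE reporting or the efficacy analysis depends on them. Most of that stands, and the omission need not have been deliberate. But the SAP never says the bullets are substitutions, and counting patients with each listed category points the other way.

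A reader might go further than the documents allow in four ways:

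- That joint cases are hidden. The plots and the listing contain all of them, and the listing shows ALP.
- That a subject with raised baseline ALT and a joint rise has no row. That subject is in the AST/ALT row; what is missing is a joint row.
- That the arms cannot be compared on potential Hy's law at all. The normal-baseline row is correctly joint, the plots show both arms, potential cases must be reported as SAEs (Protocol 8.4.2), and serious treatment-emergent events are summarised by arm (SAP 6.6.1).
- That a corrected table would match the cases sites report. The protocol also requires no evidence of hemolysis, confirmation on repeat testing and no other cause yet found, and leaves widely separated rises to judgement. A programmed laboratory screen applies none of these.

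**Conclusion.** The point holds as a mismatch between Protocol 8.4.2 and SAP 6.6.3, confined to subjects with ALT, AST or TBILI above ULN at baseline. As written, the SAP mixes isolated and joint elevations in single-test rows, drops the ALP condition, and gives no by-arm count of subjects meeting the joint laboratory criteria in this subgroup. The plots and listing allow cases to be found by hand but do not supply that count.

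The size cannot be derived. The documents give neither the share of subjects with a raised baseline test nor how often one criterion is met without the other; eligibility limits show only that the subgroup is possible. A reader might infer a large overcount by assuming each criterion is met independently by some percentage of subjects. No such percentage is documented, independence is doubtful for two tests that can rise together in liver injury, and positive correlation would shrink the multiple. The conclusion needs no such figure. It rests only on reading the SAP bullets as the separate categories they appear to be.

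**What to change.** In SAP 6.6.3, restore the protocol's linking sentence and replace the two sub-bullets with one joint row for subjects with any of ALT, AST or TBILI above ULN at baseline. The row counts those who on treatment meet the AST/ALT criterion AND the TBILI criterion AND have ALP below 2×ULN or missing. Each test above ULN at baseline takes the protocol's adjusted threshold; any other test takes the standard one (above 3×ULN for AST/ALT, above 2×ULN for TBILI).

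Keep single-test rows only if labelled as isolated elevations. Show the by-arm total of normal-baseline and abnormal-baseline laboratory-criteria cases. Add a footnote that this screen does not apply the hemolysis, repeat-test and alternative-cause conditions, so it need not equal the site-reported cases. While editing, correct the sentence in the same section that names four tests and then refers to three.

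The cost is one SAP edit and a programming change. All the laboratory values are already collected, and nothing in the clinical handling of cases changes.

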### **6.6.4. Vital Signs**

Vital signs data includes weight, pulse, systolic blood pressure, and diastolic blood pressure. Measurements were only to be provided once per timepoint. If multiple assessments are provided per timepoint, the maximum value will be used for reporting.

Vital signs data will be summarized using simple descriptive statistics (mean, standard deviation, median, quartiles, minimum, and maximum) of actual values and change from baseline for each nominal visit over time (ie, unscheduled assessments will be excluded). The total number of patients for change from baseline will include all patients in the treatment arm who have both a baseline value and a value at the nominal visit. Baseline will be selected as defined in [Section 3.4](#).

The number and percent of patients in each of the following minimum and maximum blood pressure, body weight, and pulse categories will be presented:

- Increase in Systolic Blood Pressure  $\geq 40$  mmHg.
- Decrease in Systolic Blood Pressure  $\geq 40$  mmHg.
- Decrease in Systolic Blood Pressure  $\geq 60$  mmHg.
- Increase in Diastolic Blood Pressure  $\geq 20$  mmHg.
- Decrease in Diastolic Blood Pressure  $\geq 20$  mmHg.
- Decrease in Diastolic Blood Pressure  $\geq 40$  mmHg.
- Decrease in Body Weight  $\geq 10\%$ .
- Maximum Pulse Rate  $> 120$  bpm.
- Minimum Pulse Rate  $< 50$  bpm.
- Maximum increase in pulse rate  $\geq 30$  bpm.
- Maximum decrease in pulse rate  $\geq 30$  bpm.

All assessments, including unscheduled assessments will be considered. A patient can be included in multiple categories if different criteria are met at different timepoints.

